## 5. **Vasopressor/inotrope-free days to day 28**

- An ordinal outcome of the number of days alive and free of vasopressor/inotropes. This is the exact calculation of OSFD, with vasopressor/inotropes as the only organ support category. In-hospital death is considered a 0 (consistent with ACTIV-4A protocol 1.0).
- All platforms compute vasopressor-free days based on integer days on which vasopressors/inotropes were not received at any time
- Vasopressor/inotrope-free days will be computed based on the duration of time from the initiation of vasopressors/inotropes to the final cessation of vasopressors/inotropes during the 28-day period; intervening days on which patients are not on vasopressors/inotropes will be ignored

## 6. **Ventilator-free days to day 28**

- An ordinal outcome of the number of days alive and free of ventilation. This is the exact calculation of OSFD, with invasive or non-invasive ventilation as the only organ support category. In-hospital death is considered a 0 (consistent with ACTIV-4A protocol 1.0).
- All platforms compute ventilator-free days based on integer days on which invasive or non-invasive ventilation were not received at any time.
- Ventilator-free days will be computed based on the duration of time from the initiation of invasive or non-invasive ventilation to the final cessation of invasive

or non-invasive ventilation during the 28-day period; intervening days on which patients are not on ventilatory support will be ignored.

**7. Renal replacement-free days to day 28**

- Restricted to patients not on Renal Replacement Therapy at baseline
- An ordinal outcome of the number of days free of renal replacement therapy in the hospital. Death is considered a 0 (consistent ACTIV-4A protocol 1.0).
- Compute renal replacement-free days based on integer days on which renal replacement therapy was not received at any time
- Renal replacement-free days will be computed based on the duration of time from the initiation of renal replacement therapy to the final cessation of renal replacement therapy during the 28-day period; intervening days on which patients are not on renal replacement therapy will be ignored

**8. Time to ICU Liberation**

- Time until the last day in the ICU (including days between ICU stays not in the ICU). This variable will be truncated at 90 days.
- Patients who die in ICU at any time will be considered censored at 90 days.
- Patients still in the ICU at data snapshot will be considered censored at the time of exposure (at the time the snapshot was taken).

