#### 4.3. Primary Endpoint

The primary endpoint for the study is *organ support-free days* (OSFD). The endpoint is the number of days, out of the first 21 days after randomization, that a patient is alive and free of ICU-level organ support. For the purposes of the calculation of OSFDs, if a patient dies during their index hospitalization they will be considered the status of dead even if the death occurs after the first 21 days, through 90 days. If a patient dies during their acute index hospitalization they are coded as having  $-1$  OSFDs, which is the worst outcome for the measure. Any patient on ICU-level organ support for all of the first 21 days that does not die, will be labeled as  $0$  OSFDs, the second worst outcome. The number of days is rounded to the nearest day, creating an integer valued outcome. The values of  $0, 1, \dots, 21$  refer to the number of days alive and free of organ support, with smaller values being worse outcomes. Therefore, the primary outcome OSFDs is an ordinal outcome with 23 possible outcomes for each patient,  $-1, 0, 1, 2, \dots, 21$ . The details for the calculation of the endpoint is detailed in the data dictionary.

ICU-level of organ support is defined as high flow nasal cannula, non-invasive ventilation, invasive ventilation, extracorporeal life support, vasopressors, and/or inotropes delivered in an ICU or repurposed critical care area; high flow nasal cannula is considered to be organ support when applied inspiratory flow is  $\geq 20$  L/min and  $\text{FiO}_2 \geq 0.4$ . Due to the varying provision of organ-support in potentially repurposed areas during the pandemic, ACTIV-4a defines any hospitalized area able to deliver the above organ-support as an ICU. The details for the calculation of the endpoint is detailed in the data dictionary.

This primary endpoint is an ordinal outcome and the primary analysis model analyzes the outcome as ordinal, with a cumulative logistic proportional odds model. The details of the primary analysis model are presented in Section 12.1. The measure of relative efficacy for the interventions is an odds ratio (OR) which captures the effect of having improved outcomes in OSFDs across the scale between the two interventions. The model is structured so that for P2Y12 an  $\text{OR} > 1$  implies improved outcomes on OSFDs for the P2Y12 intervention compared to the control.

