**9. Duration of hospital stay**

- A time-to-event endpoint of leaving the hospital alive. If a patient is known to leave and return to the hospital within 21 days that intervening time will be ignored.
- This variable will be truncated at 90 days.
- Patients who die in hospital at any time will be considered censored at 90 days.
- Patients still in the hospital at data snapshot will be considered censored at the time of exposure. (at the time the snapshot was taken).

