#### 12.4. Analytic Approach for Secondary Time-To-Event Endpoints

All inferential time-to-event analyses will be done using a Bayesian piecewise exponential model. The Bayesian time-to-event model is intended to mirror a Cox proportional hazards model, with the underlying hazard rate modeled with a piecewise exponential model. The underlying hazard will be modeled with a hazard rate for each 10-day period in the model. The prior distribution for the hazard rate for each day is a gamma distribution with 1 day of

exposure and a mean equal to the total exposure divided by the total number of events. This prior will have very little weight but will provide numerical stability to the model. Each factor is incorporated as a proportional hazard rate through an additive linear model of the log-hazard. The default prior for each factor is the same as for the log-odds in the ordinal model. If other non-specified variables are added to the model, then a normal distribution with mean 0 and standard deviation 10 will be utilized.

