### [12.7. Model Outputs](#)

The standard model outputs for each treatment effect will be the mean, standard deviation, median, and 95% credible intervals (all credible intervals will be equal-tailed intervals, so 95% credible intervals will range from the 2.5th percentile to the 97.5th percentile of the posterior distribution). For the ordinal endpoints, the odds ratios will be summarized. For the dichotomous endpoints, the odds ratios will be summarized. For the time-to-event endpoints, the hazard ratios will be summarized. **For consistency, all models will be parameterized so that an odds ratio or hazard ratio greater than 1 indicates clinical benefit.**

For each inferential model, a posterior probability that one arm is superior will be provided for each comparison between arms. This posterior probability has been identified as the primary analysis metric between arms. A posterior probability greater than 99% of superiority or inferiority has been identified as statistically significant. For futility a threshold of 95% has been specified.

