#### [12.9. Handling of missing data](#)

For the primary endpoint of OSFDs missing primary outcomes will be ignored. A sensitivity analysis is conducted where last status carried forward is used for imputation. Patients with missing age, date of randomization, sex or treatment assignment will be ignored. For additional endpoints those patients missing the endpoint will be ignored (for time to event analyses censoring will be used and aren't considered missing). For the subgroup analyses patients with missing subgroup variables will be lumped into a single group of "missing" in addition to the subgroup classifications.

For time-to-event analyses patients that have a competing event that dictates they cannot achieve a positive outcome (like death for time to hospital discharge), the patient will be assigned a no positive event outcome at the maximum time for the analysis. Patients not achieving an absorbing event that become lost-to-follow up will be censored at the last known time (unless otherwise specified for the analysis).

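### Time to ICU liberation (SAP section 7, endpoint 8) counts a patient who leaves the ICU and then dies on a ward as liberated, which biases the hazard ratio if place of death differs by arm

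*SAP*

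**What the plan says.** SAP section 7, endpoint 8 measures time to the last ICU day, counts days between ICU stays, and truncates at day 90. Its only rule on death is "Patients who die in ICU at any time will be considered censored at 90 days". It does not require the patient to be alive afterwards, and it has no rule for death on a ward after the last ICU day. It names no population and does not say how a patient who never enters an ICU is handled.

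The next endpoint, Duration of hospital stay, is built differently. It is "A time-to-event endpoint of leaving the hospital alive", and its death rule is "Patients who die in hospital at any time will be considered censored at 90 days". The primary endpoint (sections 4.3 and 7) likewise scores in-hospital death as the worst value, wherever in the hospital it occurs, through day 90.

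Three other provisions bear on the reading:
- Section 12.9 assigns no positive event, at the maximum time, to "patients that have a competing event that dictates they cannot achieve a positive outcome (like death for time to hospital discharge").
- Section 12.7 states that "all models will be parameterized so that an odds ratio or hazard ratio greater than 1 indicates clinical benefit".
- Section 4.3 states that "ACTIV-4a defines any hospitalized area able to deliver the above organ-support as an ICU".

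**The concern.** Leaving the ICU is a good outcome only if the patient is getting better. Some patients leave because care has been limited, or leave and then deteriorate, and die on a ward. Endpoint 8 records such a patient as liberated on the last ICU day, exactly like a survivor. The same death in an ICU bed would be held as not liberated to day 90, so the patient's contribution depends on the place of death.

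The trial is open label (Protocol 4.1). Protocol A2.1 asks for local outcome assessors who are blinded to assignment, but that does not blind the clinicians who decide when a patient leaves the ICU. If those decisions differ by arm, the hazard ratio moves toward the arm with more ward deaths, and part of an excess in mortality can be hidden or appear as faster liberation.

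**Working it through.** **Does another rule catch the case?** Section 12.9 applies when the competing event makes the positive outcome unattainable. Death in the ICU does that for liberation. Death on a ward after the last ICU day comes after the event has occurred, so 12.9 leaves it as a liberation. Endpoint 9 does not have the gap, because its event requires discharge alive and its death rule covers the whole hospital.

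**Size.** The SAP gives no event rate, power or place-of-death figure for this endpoint, so there is no stated figure to reproduce. What follows is illustrative.

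Assumed inputs, none from the documents: in-hospital mortality *m*; share *s* of deaths that occur on a non-ICU ward; lognormal ICU time with median 9 days and sigma 0.7, the same for survivors and ward deaths. The control arm has *m* = 0.30 and *s* = 0.10.

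Taken from the SAP: a 90-day horizon and a piecewise-exponential proportional-hazards model as in section 12.4 ("The underlying hazard will be modeled with a hazard rate for each 10-day period in the model"), fitted by maximum likelihood without covariates or priors, on at least 300,000 simulated patients per arm.

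Proportion counted as liberated:
- as written: 1 − *m*(1 − *s*); control: 1 − 0.30 × 0.90 = 0.730
- with all in-hospital deaths held to day 90: 1 − *m*; control: 0.70

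| Treated arm *m*, *s* | Liberated as written | HR as written | HR, all in-hospital deaths held |
|---|---|---|---|
| 0.30, 0.10 | 1 − 0.270 = 0.730 | 1.00 | 1.00 |
| 0.30, 0.15 | 1 − 0.255 = 0.745 | 1.04 | 1.00 |
| 0.30, 0.25 | 1 − 0.225 = 0.775 | 1.12 | 1.00 |
| 0.33, 0.10 | 1 − 0.297 = 0.703 | 0.93 to 0.94 | 0.93 |
| 0.33, 0.15 | 1 − 0.2805 = 0.7195 | 0.97 | 0.93 |
| 0.33, 0.30 | 1 − 0.231 = 0.769 | 1.10 | 0.93 |

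A Cox fit on 60,000 patients per arm gave 1.10 and 0.99 for the third row, and 1.10 and 0.94 for the last.

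**Break-even.** With mortality of 30% versus 33%, the excess disappears from the endpoint when the ICU-death proportions are equal: 0.33(1 − *s*) = 0.27, so *s* = 1 − 0.27/0.33 = 0.18. The simulated hazard ratio at *s* = 0.18 is 1.00. Beyond that share, the arm with more deaths looks better.

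**Extra deaths in one place only.** This uses a second set of assumptions: gamma ICU times with mean 10 days, and a control arm with 25% ICU deaths and 5% ward deaths.
- Five extra points of mortality, all on the ward (25% + 10%): 1.00 as written, or 1.02 if patients who die on the ward leave the ICU earlier (mean 3 or 6 days). The corrected value is 0.88 to 0.89.
- Five extra points, all in the ICU (30% + 5%): 0.89 under both rules.

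**The case against.** A reader might infer that more deaths will generally read as faster recovery. The documents do not support that. The distortion needs a ward share that differs by arm, and nothing in the documents predicts one. With equal shares the two rules agree closely: at 10% in both arms, both give about 0.93 for mortality of 30% versus 33%; at 20% in both arms, 0.94 as written and 0.93 corrected. Extra ICU deaths lower the hazard ratio as they should. This stands, and the point is conditional.

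The broad ICU definition in section 4.3, if it carries over to endpoint 8, makes deaths in any area able to deliver organ support ICU deaths. That shrinks the affected group by an unknown amount. It does not empty it, because deaths in areas without that capability remain.

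A reader might also call endpoint 8 a contradiction of endpoint 9. It can be defended: each holds to day 90 the deaths that preclude its own event. The two rules define different estimands, ICU exit versus ICU exit with survival of the admission. What remains is that the first is read as clinical benefit with no provision for later death in the same admission.

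The consequence is limited. The endpoint is absent from the secondary list in Protocol 4.2.2 and from the expedited-report list in SAP 3.1, and it is not a superiority or futility trigger (SAP 4.4 and 12.13). In-hospital, 28-day and 90-day mortality are analysed separately, so a reader would see an excess of deaths elsewhere.

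Finally, the silence about patients never admitted to an ICU might suggest that the moderate cohort must be dropped. It does not. Whether such patients would be treated as missing or as liberated at time zero is a guess, and the two choices would act differently. The silence calls for a stated rule only.

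**Conclusion.** The point holds as a gap in one secondary endpoint. As written, death on a non-ICU ward during the index hospitalization counts as liberation, section 12.9 does not correct this, and endpoint 9 and the primary endpoint treat such deaths differently. If the ward share of deaths differs by arm, the hazard ratio is biased toward the arm with more ward deaths. On the assumed figures the bias runs from about 0.04 on the hazard ratio (ward share 10% versus 15%, equal mortality) to about 0.17 (10% versus 30%, mortality 30% versus 33%: 1.10 − 0.93). It is 0.01 or less when the share is 10% in both arms. These sizes rest on mortality, ward shares and ICU times that the documents do not give. The primary conclusion and the adaptive decisions are not affected.

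**What to change.** In SAP endpoint 8, widen the death rule from deaths in the ICU to any death during the index hospitalization, in whatever location, through day 90, with those patients held as not liberated at day 90. This matches endpoint 9. It needs one wording change and no new data, because in-hospital death through day 90 is already an endpoint. The cost is a change of estimand: the endpoint becomes ICU exit with survival of the index hospitalization, and the SAP should describe it that way.

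The SAP should also state how patients never admitted to an ICU enter this endpoint. The rule should not exclude them on the basis of ICU admission after randomization, since that would select on a post-randomization event. The endpoint can stay in place for the moderate cohort.

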**9. Duration of hospital stay**

- A time-to-event endpoint of leaving the hospital alive. If a patient is known to leave and return to the hospital within 21 days that intervening time will be ignored.
- This variable will be truncated at 90 days.
- Patients who die in hospital at any time will be considered censored at 90 days.
- Patients still in the hospital at data snapshot will be considered censored at the time of exposure. (at the time the snapshot was taken).

**10. Major bleeding on or before day 15**

- A dichotomous endpoint of major bleeding as defined according to the “International Society of Thrombosis and Hemostasis (ISTH) criteria in non-surgical patients.”
- The endpoint is censored at 15 days to correspond to the intervention duration.

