The table shows the preferred dosing for P2Y12 inhibitor treatment. Ticagrelor is the preferred P2Y12 inhibitor, but any of the following strategies are acceptable.

Age	Weight	Ticagrelor#	Prasugrel*	Clopidogrel
<75 years	<60 kg	no load; 60 mg BID	no load, 5 mg daily	300 mg load**, then 75 mg daily
	≥60 kg		30 mg load**, 10 mg daily	
≥75 years	<60 kg	no load; 60 mg BID	not recommended	300 mg load**, then 75 mg daily
	≥60 kg		no load, 5 mg daily	

The preferred P2Y12 inhibitor is ticagrelor, which has a rapid onset of action without the need for a loading dose, unless there is a concern about drug-drug interactions (see Manual of Operations). The 60 mg twice daily dose is recommended; *If ticagrelor 60 mg is not available, 90 mg dose, may be used.* If ticagrelor is not available or is not preferred locally, prasugrel or clopidogrel may be used, preferably with a loading dose, taking into account relevant drug-drug interactions (see Manual of Operations).

if a participant will be continued on aspirin in addition the assigned P2Y12 inhibitor, aspirin dose must be ≤100 mg when administered with ticagrelor

* Prasugrel is NOT permitted in anyone with a prior stroke or TIA

**The loading dose is preferred because the average time to therapeutic effect with clopidogrel is 5 days without a loading dose, and for prasugrel is 3 days without a loading dose. A loading dose is not required.

The first dose should be administered as soon as possible after randomization.

A7.3.3. Participants previously taking aspirin before randomization

Participants taking aspirin before randomization are permitted to continue or stop aspirin therapy at the discretion of the treating physician. If a patient is randomized to Arm C and chronic ASA is continued per MD judgment, the recommended dose is 80-100 mg daily; the dose MUST be ≤100 mg daily when administered with ticagrelor.

A7.4 Duration of treatment

It is recommended that participants be given prophylactic-dose anticoagulation and a P2Y12 inhibitor daily for at least 14 days or until hospital discharge, whichever comes first. Treatment may

continue beyond 14 days at the discretion of the most responsible physician. At the time of treatment discontinuation, standard of care antithrombotic prophylaxis should be administered.

A7.5 Discontinuation of study intervention

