^{****}Strongly recommended as part of routine care, all values collected should be recorded

^{*****}Optional, listed in case report form

[#]or 14 days, whichever is earlier

[#]Participants may be assessed for functional status and quality of life that reflects baseline status pre-COVID illness and functional status and quality of life at 90 days, when contacted to ascertain vital status. (Instruments detailed in the manual of operations).

⁺Assessments indicated in the table above will be ascertained at discharge, or at 28 days, whichever comes first. Participants must be followed for vital status until discharged from the hospital or another care facility (if transferred on organ support) up to 90 days. To maximize retention, participants will be contacted intermittently post-discharge and that contact will be recorded in the EDC

⁺⁺Participants may be contacted to ascertain vital status.

A7.7 Potential Risks & Benefits

A7.7.1 Known Potential Risks

Participants are monitored as per standard of care to minimize the risk of bleeding or developing clots. The standard of care plus P2Y12 inhibitor group will receive both anticoagulation and antiplatelet therapy and thus may be at higher risk of bleeding.

A7.7.2 Known Potential Benefits

Accruing data suggest that platelets are hyperactive in the setting of COVID-19. The platelet transcriptome isolated from hospitalized patients with COVID-19 is more pro-inflammatory than the platelet transcriptome from matched controls without COVID-19. Additionally, biomarkers of platelet activity are correlated with incident thrombosis and all-cause mortality. This arm seeks to test the hypothesis that there is a benefit of antiplatelet therapy in addition to standard of care for decreasing adverse events, including macro and micro-thrombosis. This potential benefit is hypothesized to offset an increase in bleeding risk. All participants will be closely monitored by the study team and any changes in antiplatelet therapy will be discussed with the treating physicians

and/or clinical team. There is a potential direct benefit of identifying thrombus or bleeding more rapidly based on close study monitoring. This trial will contribute to the body of generalizable knowledge about the antiplatelet strategy to minimize the risk of thrombus and adverse events in patients with COVID-19.

A7.8 Event Adjudication

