#### 3.1. Reporting strategy

This SAP describes the planned analyses for the study. As outlined below, two cohorts (moderate illness, severe illness) may report at different times. Multiple reports describing the results of analysis may be prepared and published to ensure expedited dissemination of the study findings. It is anticipated that for each cohort, expedited, potentially preliminary reports will describe key primary and secondary findings and limited subgroup analyses.

Endpoints to be reported in these reports include:

- Organ support-free days to day 21 (primary endpoint)
- In-hospital mortality (key secondary endpoint)
- Major thrombotic events or death (key secondary endpoint)
- ISTH major bleeding (key safety endpoint)

Comprehensive reports providing complete characterization of trial results may subsequently be prepared and published.

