**11. Fatal bleeding 5**

- A dichotomous endpoint of fatal bleeding defined as death attributable to bleeding according to the site investigator reporting or as judged via central adjudication.
- The endpoint is counted only for bleeding events occurring within 15 days to correspond to the intervention duration. Death from that bleeding event occurring after 15 days is included here.

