There is a hierarchy of clinical importance of various TEs, with DVT in the absence of PE the least important and PE, stroke, systemic arterial embolism, and MI (all of which will be adjudicated) more clinically important. PE that impacts oxygenation or hemodynamics may impact the primary endpoint. The trial should not stop before a determination of a difference or not on the primary outcome has been reached, unless one of the two arms presents a clear safety risk, outweighing any potential efficacy benefit.

To aid the DSMB in the risk/benefit and safety determination the following analyses will be presented:

Safety Event	Quantity	P2Y12	Standard Care
ISTH Major Bleeding Events	Number of Events	X1	X2
	Number At 28-days	N1	N2
	Event Rates	X1/N1	X2/N2
	95% Confidence Interval (CI)	LB1, UB1	LB2, UB2
	Difference in Rates	Difference; 95% CI	
	Odds-Ratio	OR; 95% CI	
ICH and Fatal Bleeds	Number of Events	X1	X2
	Number At 28-days	N1	N2
	Event Rates	X1/N1	X2/N2
	95% Confidence Interval (CI)	LB1, UB1	LB2, UB2
	Difference in Rates	Difference; 95% CI	
	Odds-Ratio	OR; 95% CI	
Major Thrombotic Events (TE)*	Number of Events	X1	X2
	Number At 28-days	N1	N2
	Event Rates	X1/N1	X2/N2
	95% Confidence Interval (CI)	LB1, UB1	LB2, UB2
	Difference in Rates	Difference; 95% CI	
	Odds-Ratio	OR; 95% CI	
All-Cause Mortality	Number of Events	X1	X2
	Number At 28-days	N1	N2
	Event Rates	X1/N1	X2/N2
	95% Confidence Interval (CI)	LB1, UB1	LB2, UB2
	Difference in Rates	Difference; 95% CI	
	Odds-Ratio	OR; 95% CI	

\*PE, stroke, systemic arterial embolism, and MI

These analyses are in addition to the efficacy and futility analyses that will be presented for the primary efficacy endpoint of organ-support free-days.

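### The headline major-bleeding endpoint stops at day 15 on a treatment-duration rationale that does not fit Arm C, while its paired thrombotic composite and the DSMB table run to day 28 or longer

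*SAP*

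**What the plan says.** SAP section 3.1 lists ISTH major bleeding as the key safety endpoint of the expedited reports, next to major thrombotic events or death, and gives no window there. Section 7 supplies it. Endpoint 10 covers major bleeding up to day 15, with the reason "The endpoint is censored at 15 days to correspond to the intervention duration". Endpoint 11 does the same for fatal bleeding: "The endpoint is counted only for bleeding events occurring within 15 days to correspond to the intervention duration". A later death from a bleed inside that window still counts.

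On treatment duration, protocol A7.4 (Arm C) recommends prophylactic anticoagulation and "a P2Y12 inhibitor daily for at least 14 days or until hospital discharge, whichever comes first". It then says treatment may "continue beyond 14 days at the discretion of the most responsible physician". A footnote to the A7.6 schedule, apparently attached to study treatment, reads "or 14 days, whichever is earlier".

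The paired outcome, major thrombotic events or death, is given more than one window:
- Protocol 4.2.2: in hospital or at 28 days, whichever is earlier.
- SAP 12.13, key secondary endpoint: in hospital or at 28 days.
- SAP 12.13, safety monitoring text: day 28 or discharge, whichever is first.
- SAP section 7, endpoint 18: any time in the index hospitalization, with no day limit.

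The DSMB table in SAP 12.13 sets ISTH major bleeding against a denominator labelled "Number At 28-days".

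**The concern.** The day-15 limit rests on one reason, that it matches how long patients are treated. In Arm C that reason fits the recommended minimum course but not the longer treatment the protocol allows. A patient who stays on the P2Y12 inhibitor and has a major bleed on day 20 counts as having no bleed in endpoint 10. A pulmonary embolism on day 20, while still in hospital, counts as an event in the thrombotic composite.

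These two results are meant to be read together. SAP 12.13 frames the key secondary goal as learning whether the drug lowers thrombotic events and raises bleeding. Different windows weaken that reading. Using one name for a day-15 endpoint and a row with 28-day denominators also means that the DSMB figures and the published figures may differ without explanation.

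**Working it through.** The SAP gives no bleeding rate by day, no sample size and no count of patients treated beyond day 14. There is no plan figure to reproduce. The check is a comparison of windows, followed by an illustration.

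**1. Windows side by side**

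| Item | Source | Window |
|---|---|---|
| ISTH major bleeding | SAP 7, endpoint 10 | to day 15 |
| Fatal bleeding | SAP 7, endpoint 11 | bleed within 15 days |
| Recommended treatment, Arm C | Protocol A7.4 | at least 14 days or to discharge; may continue |
| Organ support-free days | SAP 4.3 | 21 days; in-hospital death to day 90 |
| Thrombotic composite | SAP 12.13 | 28 days or discharge |
| Thrombotic composite | SAP 7, endpoint 18 | whole index stay |
| ISTH major bleeding, DSMB table | SAP 12.13 | 28-day denominators |

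Every headline efficacy window passes day 15; the headline bleeding window does not. Day 15 covers 15/28 = 54% of a 28-day window and leaves out 13/28 = 46%.

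**2. Does another section 7 endpoint fill the gap?** Endpoints 28 and 32 count only critical or fatal bleeds to day 28, combined with death. Endpoint 33 includes ISTH major bleeds to day 28, combined with death and any thrombotic event. Endpoint 20 is titled intracranial hemorrhage and runs to 28 days, but its definition line describes ischemic stroke, and it would in any case be only one part of major bleeding. None is ISTH major bleeding on its own.

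**3. Direction.** Write RD for the risk difference, drug minus control. Then RD(to day 28) = RD(to day 15) + RD(days 16 to 28). The day-15 result understates the 28-day excess by exactly the second term. That term is positive only if an excess persists after day 15.

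**4. Illustration (assumed hazard shapes, not document figures).** If F(t) is the cumulative bleeding risk, the share of 28-day bleeds that falls after day 15 is 1 − F(15)/F(28).
- Constant hazard: 13/28 = 46%.
- Hazard with half-life h, where k = ln 2/h: (e^(−15k) − e^(−28k)) / (1 − e^(−28k)). For h = 14, 10, 7, 5 and 3 days this gives 30%, 25%, 18%, 11% and 3%.

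Protocol A7.1 puts bleeding risk in severe patients below 2%, without a time window. Taking 1% to 2% as an assumed 28-day risk:
- Low end: 1,000 × 0.01 × 0.03 = 0.3 bleeds omitted per 1,000 patients.
- High end: 1,000 × 0.02 × 0.464 = 9.3 per 1,000.

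For the contrast, assume 28-day risks of 2% and 4% with the same time pattern in both arms. The 28-day excess is 20 per 1,000. The excess visible at day 15 would be 20 × (1 − 0.03) = 19.4 to 20 × (1 − 0.464) = 10.7 per 1,000.

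**5. Inpatient time (assumed exponential stay).** With a median stay of 10, 14 or 20 days, the share still in hospital at day 15 is 2^(−15/median) = 35%, 48% or 59%. The share of inpatient days to day 28 that falls after day 15 is 24.5%, 30% or 35%. These are inpatient days, not days on drug, so they do not measure the number of on-treatment bleeds missed.

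**The case against.** A safety window tied to the planned course is a recognised choice. Day 15 fits a 14-day course that starts on the day of randomization or the day after. A longer window takes in bleeds unrelated to the drug. This stands as a reason to keep the day-15 count. It does not repair the stated rationale where longer treatment is allowed.

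A reader might infer that the plan is tilted toward the drug. The documents do not support that. The cut applies equally to both arms, and step 3 shows that the direction depends on what happens after day 15, on which there is no information.

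A reader might also infer that late bleeds go unseen. They do not. On its natural reading the DSMB table covers ISTH major bleeding, and intracranial and fatal bleeds, to 28 days. Endpoints 32 and 33 put thrombosis, bleeding and death in one common 28-day window. The gap is in the headline report, not in monitoring.

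Two limits on scope also stand. The duration text is from Arm C; the moderate-cohort appendix (Arm D) is retired and its text is not in the protocol, so the conflict is shown for the severe cohort only. And the A7.6 footnote can be read as a 14-day cap, but in the text available its symbol does not match the one on the study-treatment cell, so that link is inferred.

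**Conclusion.** The point holds for reporting. In Arm C the reason given for the day-15 limit does not cover treatment that A7.4 permits. Major bleeds after day 15 on that treatment are left out of the headline bleeding result, and no standalone ISTH major bleeding endpoint in SAP section 7 picks them up. The thrombotic composite reported beside it runs longer, and the DSMB row carries the same name with a different denominator window.

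The consequence is conditional: if a bleeding excess persists after day 15, the headline comparison understates it. Its size cannot be determined from the documents. The range of 0.3 to 9 omitted bleeds per 1,000 rests on an assumed 28-day risk of 1% to 2% and on assumed hazard shapes, and shows only that the effect could be negligible or material. Confidence is high on the window mismatch and low on how much it matters. The change is worth making before unblinding.

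**What to change.** 1. Add standalone ISTH major bleeding and fatal bleeding through day 28 or discharge, whichever is first, to SAP section 7. Name them in section 3.1 as the key safety result reported with the thrombotic composite.
2. Keep the day-15 counts as a labelled on-treatment analysis.
3. Put the window in the name wherever ISTH major bleeding appears, and state in the DSMB table the period over which events are counted as well as the denominator.
4. Align endpoint 18 with the 28-day-or-discharge window in SAP 12.13, so that the paired results share one window.
5. Reconcile protocol A7.4, the A7.6 footnote and the rationale in endpoints 10 and 11 on treatment duration. This review takes no position on which duration is right.

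The cost is mostly SAP wording, with a protocol clarification for item 5. Endpoints 28, 32 and 33 already need bleeding data to day 28, so no new collection is implied. The drawback is that some late bleeds unrelated to the drug may slightly dilute the contrast; the retained day-15 analysis shows whether they do.
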